### 6.12.2.1. Adverse Events

An overview of AEs including deaths, SAEs, TEAEs, and patients discontinued from study due to an AE will be summarized for the treatment period. Treatment Period includes all of three period: Dose-adjustment period, Primary treatment period and Maintenance treatment period.

By patient listing of all AEs, AEs leading to study treatment discontinuation, AEs leading to temporary study drug interruption and COVID-19 related AEs will be provided.

### 6.12.2.2. Serious Adverse Events

Consistent with the International Conference on Harmonisation (ICH) E2A guideline, an SAE is any AE that results in one of the following outcomes:

- Death
- Initial or prolonged inpatient hospitalization
- A life-threatening experience (that is, immediate risk of dying)
- Persistent or significant disability/incapacity
- Congenital anomaly/birth defect
- Considered significant by the investigator for any other reason.

By-patient listing of patients who experienced any SAE will be developed.

### 6.12.2.3. Treatment-emergent Adverse Events

Adverse events will be considered TEAEs if the AEs begin or increase in severity after the patient receives the first dose of baricitinib and up to the last visit during the treatment period. The MedDRA Lowest Level Term (LLT) will be used in defining which events are treatment-emergent. The maximum severity for each LLT during the baseline period up to first dose of the study medication will be used as baseline. The treatment period (i.e. Dose-adjustment period, Primary treatment period and Maintenance treatment period) will be included as post-baseline for the analysis. If an event is pre-existing during the baseline period but it has missing severity, and the event persists during the treatment period, then the baseline severity will be considered mild for determining any post-baseline treatment-emergence (ie, the event is treatment-emergent unless the severity is coded mild post-baseline); if an event occurring post-baseline has a missing severity rating, then the event is considered treatment-emergent. All TEAEs will be summarized by SOC and PT.

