10.2. Populations for Analyses

For purposes of analysis, the following populations are defined:

Population	Description
Enrolled	All subjects who sign informed consent or assent (as applicable), and meet all eligibility criteria
Full analysis set	All enrolled subjects who take at least 1 dose of study treatment.

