## 6.3. Use of an “Efficacy Subset” of Patients

**Entered population** set includes those patients who sign the informed consent form directly or through their legally acceptable representatives.

**Enrolled population** set includes all patients who have entered the study and who are not considered screen fails at or before Visit 6 (i.e. patients not excluded due to not meeting inclusion criteria or meeting exclusion criteria during screening/pre-treatment period).

**Efficacy population** set includes all enrolled patients who have at least one dose of baricitinib.

**Safety population** set includes all enrolled patients who receive at least 1 dose of baricitinib and who did not discontinue the study for the reason “Lost to Follow-up” at the first postbaseline visit (Visit 7).

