### 6.12. Safety Analyses

All safety data will be descriptively summarized by disease diagnosis for the safety population. The safety outcomes include TEAEs, TEAEs related to study drug, adverse events of special interest (AESI), serious AEs (SAEs), laboratory analytes, and vital signs.

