## 6.12.2. Adverse Events

Adverse events are classified based upon the Medical Dictionary for Regulatory Activities (MedDRA). Each AE will be coded to system organ class (SOC) and Preferred Term (PT) using the MedDRA version that is current at the time of database lock. Severity of AEs is recorded as mild, moderate, or severe. Adverse events will use the safety population defined in Section 6.3.

Summaries will consist of the frequency and percent of patients experiencing each AE. For summaries, SOC will be sorted in alphabetical order and PT in decreasing frequency within SOC by the total group. Patients will only be counted once, regardless of how many conditions are included under the same SOC and PT.

All AE listings will include AE type (pre-existing condition or TEAE), SOC, PT, reported term, event start and end date, start and end day, severity, related to study drug or non-study drug treatment, SAE status, reason AE is classified as serious, and event outcome.

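### SAP 6.3 removes a dosed patient lost to follow-up at Visit 7 from the safety population; separately, SAP 6.12.2 keeps AEs that start after the last treatment-period visit out of the main AE summaries

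*SAP*

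**What the plan says.** **Population.** SAP 6.3 restricts the safety population to enrolled patients who "receive at least 1 dose of baricitinib and who did not discontinue the study for the reason" of loss to follow-up at Visit 7. The efficacy population in the same section has no such condition: it "set includes all enrolled patients who have at least one dose of baricitinib". Protocol 10.2 defines its full analysis set as "All enrolled subjects who take at least 1 dose of study treatment". SAP 6.12 then says "All safety data will be descriptively summarized by disease diagnosis for the safety population", and SAP 6.12.2 says "Adverse events will use the safety population defined in Section 6.3".

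**Window.** SAP 6.12.2.3 counts an event as treatment-emergent if it begins or worsens "after the patient receives the first dose of baricitinib and up to the last visit during the treatment period". SAP 6.1.1 closes the treatment period at its final visit or at early discontinuation. SAP 6.12.2.1 says "An overview of AEs including deaths, SAEs, TEAEs, and patients discontinued from study due to an AE will be summarized for the treatment period", and lists three periods (dose adjustment, primary, maintenance), without post-treatment follow-up. On listings, SAP 6.12.2 says "All AE listings will include AE type (pre-existing condition or TEAE"; no third type is offered.

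The protocol records AEs from consent onward (9.2.1). It schedules Visit 801 for safety about 28 days after the last dose (Section 2, footnote x), with a ±5 day tolerance (Table JAJE.3), and holds the final lock until follow-up is complete (10.3.6).

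**The concern.** A safety set would normally be at least as inclusive as the efficacy set. Here it is narrower, the SAP gives no reason, and no other AE output picks up the patient who is removed.

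On the window, the trial collects a month of post-dose safety data and then routes new events from that month away from the displays that most readers consult. A thrombosis or infection starting after the last treatment-period visit would not reach the only AESI output that the SAP specifies. A death or SAE in that interval would not reach the overview. Both gaps come from rules that the SAP states, not from missing detail.

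**Working it through.** The plan gives no power, error rate or event-rate figure to reproduce; about 5 patients is a feasibility number (SAP 5.2). The check is to run each output against its stated restriction, then to size the two gaps.

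**1. Where an AE appears if it starts after the last treatment-period visit and by Visit 801**

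| Output | Restriction | Result |
|---|---|---|
| AE overview (SAP 6.12.2.1) | three treatment periods | absent, including deaths and SAEs |
| SOC/PT summary (6.12.2.3) | TEAEs | absent |
| AESI listing (6.12.3.1) | treatment-emergent | absent |
| Registry Other category (6.18) | TEAE and not serious | absent |
| All-AE listing (6.12.2.1) | none; listings cover all visits (6.1) | present, but neither AE type fits |
| SAE listing (6.12.2.2) | any SAE | present if serious |
| Registry Serious category (6.18) | TEAE or not | present if serious |

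An AE between the last dose and an early termination visit is inside the window. The gap opens only after that visit.

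**2. Size of the population gap (hypothetical: one patient excluded)**

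- Share of the safety denominator: 1/5 = 20%. In a two-patient disease group: 1/2 = 50%.
- If that patient had the only event, 1/5 (20%) would be reported as 0/4 (0%).
- If no events were seen, the one-sided 95% upper bound is 1 − 0.05^(1/n): 45.1% for n = 5 and 52.7% for n = 4.

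For the registry tables the exclusion is an inference, because SAP 6.18 names no population.

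**3. Size of the window gap**

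Let d be the days from last dose to Visit 801 (28 ± 5, so 23 to 33). Let L be the days from last dose to the last treatment-period visit. The documents do not give L, so it is varied as an assumption. The gap is max(0, d − L).

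| L (days) | Gap per patient (days) | Five patients, all attending Visit 801 (patient-days) |
|---|---|---|
| 0 | 23 to 33 | 115 to 165 |
| 7 | 16 to 26 | 80 to 130 |
| 14 | 9 to 19 | 45 to 95 |
| 33 or more | 0 | 0 |

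As a share of calendar time from first dose to Visit 801, with T days from first to last dose, the share is (d − L)/(T + d).

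- Week 244 completer, T = 7 × 244 = 1708. L = 0: 23/1731 = 1.3% to 33/1741 = 1.9%. L = 14: 9/1731 = 0.5% to 19/1741 = 1.1%.
- Patient stopping at Week 20, T = 7 × 20 = 140. L = 0: 23/163 = 14.1% to 33/173 = 19.1%. L = 14: 9/163 = 5.5% to 19/173 = 11.0%.

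These are shares of time, not of events. Protocol 5.1 does not require Visit 801 for patients who transfer to commercial baricitinib, so the five-patient totals are upper figures.

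**The case against.** The strongest reply is that listings are a main reporting tool here (SAP 6.1), and no event in follow-up disappears from them. Each AE row carries onset date and day, severity and outcome, so with about 5 patients a reader can see that an event began after treatment. Ending TEAEs with the treatment period is also defensible, because other disease therapy is allowed during follow-up (protocol 5.1) and would blur attribution. The Visit 7 rule may never have applied: loss to follow-up needs repeated missed visits and failed contact (protocol 8.3), so such a patient would rarely have post-dose AE records. The patient would also still appear in the disposition listing, which uses the enrolled population (SAP 6.4).

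Most of this stands. It limits the size of the point and argues for keeping the on-treatment window. It does not explain why a dosed patient belongs in the efficacy set but not the safety set, or why deaths and AESIs in a scheduled safety period have no summary.

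A reader might infer more than the documents support:

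- **That follow-up events go unreported.** They do not; see the last three rows of the first table.
- **That protocol 8.1.1 and 5.1 close the window at different dates after drug is stopped.** Section 8.1.1 refers to the Schedule of Activities, whose footnote w requires an early termination visit when treatment stops before Visit 36. That largely removes the difference.
- **That protocol 10.3.4 and Appendix 1 contradict each other on TEAEs.** The first gives the start and the second a bounded treatment period; the SAP supplies the end.
- **That Visit 801 laboratory values are uncovered.** SAP 6.1.1 calls any measurement after first dose postbaseline, and SAP 6.12.4 takes abnormalities at any time postbaseline.

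**Conclusion.** Both parts hold on the text and are independent of each other. The population rule removes all SAP 6.12 AE reporting for any patient it catches. Its effect is nil if it caught nobody. The sponsor can check this now: the Week 52 lock has passed (SAP 3) and was planned for when all planned enrolled patients had reached Week 52 or left early (SAP 6.15). The window rule affects only patients followed beyond their last treatment-period visit, for at most 23 to 33 days each. It weighs more, in relative terms, for an early stopper than for a Week 244 completer. These sizes rest on the assumed L and on attendance at Visit 801. In a descriptive study of about 5 patients the practical effect is small, but the correction is specific, uses data already collected, and can still be made.

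**What to change.** In SAP Version 5, which is to be approved before the final lock:

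- **6.3:** define the safety population as all enrolled patients who take at least 1 dose of baricitinib, and delete the Visit 7 condition.
- **6.12.2:** add a follow-up AE type for events starting after the last treatment-period visit.
- **6.12.2.1:** add a separate summary of AEs, AESIs, deaths and SAEs starting after that visit and up to Visit 801, for patients who have that visit. Word it so that a patient who dies before Visit 801 is counted up to death.
- **6.12.2.3:** leave the on-treatment TEAE window as it is, so that TEAE onset rules match the earlier locks.

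The cost is a little extra output. If the safety denominator differs from the primary or Week 52 lock, the clinical study report should say so; SAP 6.1 already uses that report to record changes in analysis methods. No new data are needed.

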5.1. Overall Design

Study I4V-JE-JAJE is a Phase 2/3 multicenter, open-label study to evaluate the efficacy and safety of baricitinib in adult and pediatric Japanese patients with type 1 autoinflammatory interferonopathies expected to benefit from JAK1/JAK2 inhibition, including NNS/CANDLE, SAVI, and AGS. Patients will receive an initial dose based on weight class and eGFR. The patient's disease severity will be recorded daily in a patient diary by the patient or caregiver throughout the study. Average diary scores will characterize responses to therapy and will trigger additional dose escalation or steroid weaning (for patients who are receiving systemic corticosteroids), as appropriate. After marketing authorization of baricitinib for any of the indications in Japan, the study will be considered a postmarketing clinical trial (Phase 4 study).

The study consists of 6 periods:

Screening Period

The duration of screening period is different among diseases. For SAVI and AGS patients, the duration of the screening period is at least 7 days and up to 35 days prior to baseline (Visit 6). For NNS/CANDLE patients, they will enter the pre-treatment period after screening period. Data at Visit 6 is used for baseline in all patients. The patient or the patient's parent or a legal guardian (hereafter, "parent" refers to "parent or legal guardian") will sign the informed consent form (ICF) and assent from the patient will be obtained when appropriate (see [Appendix 3](#)) prior to any study assessments, examinations, or procedures being performed at Visit 1. Screening procedures will be performed according to the Schedule of Activities (Section [2](#)).

Patient diaries will be provided for daily collection of information regarding the patient's signs and symptoms. Patient diary collection will begin at screening and each patient (or caregiver) will complete the diary at approximately the same time every day during the screening period and for the duration of the study. Ideally, the same person will complete the diary each day. It will not be considered a protocol violation even if record time or assessor for the diary is different.

Patients who receive a purified protein derivative (PPD) skin test at screening will need to return within 48 to 72 hours later to read the skin test (Visit 1A).

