9.2.1. Serious Adverse Events

An SAE is any AE from this study that results in 1 of the following outcomes:

- death,
- initial or prolonged inpatient hospitalization,
- a life-threatening experience (that is, immediate risk of dying),
- persistent or significant disability/incapacity,
- congenital anomaly/birth defect,
- important medical events that may not be immediately life-threatening or result in death or hospitalization but may jeopardize the patient or may require intervention to prevent 1 of the other outcomes listed in the definition above. Examples of such medical events include allergic bronchospasm requiring intensive treatment in an emergency room or at home, blood dyscrasias or convulsions that do not result in inpatient hospitalization, or the development of drug dependency or drug abuse.

All AEs occurring after signing the ICF and Assent Form (as applicable) are recorded in the eCRF and assessed for serious criteria. The SAE reporting to Lilly begins after the patient has signed the ICF or Assent Form (as applicable) and has received investigational product. However, if an SAE occurs after signing the ICF and Assent Form (as applicable), but prior to receiving investigational product, the SAE should be reported to Lilly as per SAE reporting requirements and timelines if it is considered reasonably possibly related to study procedure.

Study site personnel must alert Lilly or its designee of any SAE within 24 hours of investigator awareness of the event via a sponsor-approved method. If alerts are issued via telephone, they are to be immediately followed with official notification on study-specific SAE forms. This 24hour notification requirement refers to the initial SAE information and all follow-up SAE information. Patients with a serious hepatic AE should have additional data collected using the electronic data entry system.

Investigators are not obligated to actively seek AEs or SAEs in subjects once they have discontinued and/or completed the study (the patient disposition CRF has been completed). However, if the investigator learns of any SAE, including a death, at any time after a subject has been discharged from the study, and he/she considers the event reasonably possibly related to the study treatment or study participation, the investigator must promptly notify Lilly or its designee.

Regulatory Reporting Requirements for SAEs

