10.3.4. Safety Analyses

Safety measures will be summarized and/or listed. Standard listings will include TEAEs, SAEs, and results from laboratory tests. By definition, TEAEs are AEs that begin or increase in severity after the patient receives the first dose of baricitinib. Summaries of the incidence and event counts of TEAEs and SAEs, of abnormal shifts in laboratory values, or of per-visit distributions of laboratory results will be created. Other data, including body weight and height data will be reported in patient listing. Weight, height, occipital frontal circumference measurement (children less than 3 years old), and body mass index data will be merged to the Japanese children standard growth data issued by the Japanese Association for Human Auxology to compare subjects' growth with the standard (Isojima et al. 2016).

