### 6.12.3. Deaths, Other Serious Adverse Events, and Other Notable Adverse Events

#### 6.12.3.1. Adverse Events of Special Interest

Adverse events of special interest include the following:

- Infections (all MedDRA preferred terms in MedDRA SOC “Infections and infestations”)
- myelosuppressive events
  - anemia (hemoglobin <6.5 g/dL),
  - leukopenia (White blood cell [WBC] count <2000 cells/ $\mu$ L),
  - neutropenia (absolute neutrophil count [ANC] <1000 cells/ $\mu$ L),
  - lymphopenia (lymphocyte count <500 cells/ $\mu$ L), and
  - thrombocytopenia (platelet count <75,000/ $\mu$ L)
- thrombocytosis (platelet count >600,000/ $\mu$ L)
- malignancies (except for successfully treated basal or squamous cell skin carcinoma)
- hepatic events including elevations in alanine transaminase (ALT) or aspartate aminotransferase (AST) (>3 times upper limit of normal [ULN]) with total bilirubin (>2 times ULN)
- major adverse cardiovascular events (MACE) which was positively adjudicated
- thrombotic events (such as deep vein thrombosis and pulmonary embolism) which was positively adjudicated

By-patient listing of treatment-emergent adverse events of special interest by AESI category will be developed by disease diagnosis.

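### SAP 6.12.2.3 holds two unreconciled rules for treatment emergence; under one, a resolved pre-dose event can mask a later on-drug episode of the same term

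*SAP*

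**What the plan says.** SAP 6.12.2.3 opens with an onset rule: "Adverse events will be considered TEAEs if the AEs begin or increase in severity after the patient receives the first dose of baricitinib". Protocol 10.3.4 has the same rule: "By definition, TEAEs are AEs that begin or increase in severity after the patient receives the first dose of baricitinib".

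The SAP section then adds a second rule. First, "The MedDRA Lowest Level Term (LLT) will be used in defining which events are treatment-emergent". Next, "The maximum severity for each LLT during the baseline period up to first dose of the study medication will be used as baseline". Neither sentence requires the earlier event to be still present at the first dose. The only clause that mentions persistence covers a missing baseline severity: "If an event is pre-existing during the baseline period but it has missing severity, and the event persists during the treatment period". A further clause declares a post-baseline event with missing severity to be treatment-emergent. The section does not say when the baseline period begins.

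On collection, Protocol 9.2.1 states: "All AEs occurring after signing the ICF and Assent Form (as applicable) are recorded in the eCRF and assessed for serious criteria". On reporting, SAP 6.12.3.1 states: "By-patient listing of treatment-emergent adverse events of special interest by AESI category will be developed by disease diagnosis". The infection category of AESI there covers every preferred term in the infections system organ class.

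**The concern.** Take a patient who has a mild upper respiratory infection during the pre-dose period, recovers, starts baricitinib, and later has another mild infection coded to the same LLT. The onset rule makes the second episode a TEAE. The LLT rule compares it with a baseline of mild, finds no worsening, and does not flag it. A programmer could follow either sentence.

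Infections are an event of special interest for this drug, and the AESI listing is restricted to treatment-emergent events. A rule that can remove new on-drug infections from that listing should not be left to interpretation. The effect could also differ by disease, because the pre-dose observation time differs and safety is summarised by diagnosis (SAP 6.12).

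**Working it through.** The plan gives no figure of its own on this point, so there is nothing to reproduce. The check has five steps.

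**1. The definitions side by side.**
- SAP 6.12.2.3, first sentence, and Protocol 10.3.4: onset after first dose is enough.
- SAP 6.12.2.3, second and third sentences: compare with the worst pre-dose severity of the same LLT, resolved or not.
- Protocol Appendix 1 glossary: the event was not there before treatment, or it got worse. This leans towards the second rule.

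Two clauses suggest that the second rule is more than loose drafting. Persistence is required only where baseline severity is missing. And a new event with missing severity would need no special clause if onset alone decided.

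**2. Severity combinations.** Let the pre-dose maximum be mild, moderate or severe, and the new episode mild, moderate or severe. Under the LLT rule the new episode is not flagged when its severity is at or below the maximum: 1 + 2 + 3 = 6 of 9 combinations, with 3 of 9 kept. Under the onset rule, 0 of 9 are lost. This counts cases; it is not a probability. Episodes with missing severity, or coded to another LLT, are flagged under both rules.

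**3. Outputs that depend on the flag.**
- Affected: the TEAE summary by SOC and PT (SAP 6.12.2.3), the AESI listing (SAP 6.12.3.1), and the registry Other category, which requires a non-serious TEAE (SAP 6.18).
- Not filtered on the flag: the listings of all AEs, discontinuations and interruptions (SAP 6.12.2.1), the SAE listing (SAP 6.12.2.2), and registry SAEs (SAP 6.18).
- Labelling: SAP 6.12.2 gives only two AE types in listings, pre-existing condition or TEAE. A masked on-drug event would apparently carry the first label, although its start date and study day would show its onset.

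**4. Pre-dose window, if the baseline period starts at consent.** In NNS/CANDLE, Visit 1 is at Day -91 (Protocol Section 2; 13 weeks in inclusion criterion 3). In SAVI and AGS, screening lasts 7 to 35 days (Protocol 5.1).
- Nominal ratio: 91/35 = 2.6 to 91/7 = 13.
- 12-week pretreatment period only: 84/35 = 2.4 to 84/7 = 12.
- With an assumed 28-day biologic washout added: 119/35 = 3.4 to 119/7 = 17.

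**5. Illustration with assumed rates.** The documents give no episode rates. If episodes of one LLT follow a Poisson process at rate r per year, the chance of at least one in d days is 1 − exp(−r·d/365):

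| Assumed r per year | 7 days | 35 days | 91 days |
|---|---|---|---|
| 0.5 | 1% | 5% | 12% |
| 1 | 2% | 9% | 22% |
| 2 | 4% | 17% | 39% |
| 4 | 7% | 32% | 63% |

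These are chances that a potentially masking episode occurs before dosing, not chances that an event is lost.

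**The case against.** The strongest reply is that the SAP's first sentence already settles the matter: a new episode begins after first dose, so it is a TEAE, as in Protocol 10.3.4. Loss of events then follows only from one of two readings. That is right. A reader might infer that on-drug infections definitely drop out of the TEAE outputs, and the documents do not establish this. Nor is the LLT rule plainly contrary to the protocol, since the Appendix 1 glossary is compatible with it. What stands is that the conflict is in the text and nothing resolves it.

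A second reply concerns size. A reader might take 2 episodes a year over 244 weeks (244 × 7/365.25 = 4.68 years) and infer about 9.4 lost episodes. That does not carry to the table. SAP 6.12.2 counts a patient once per SOC and PT, so each masked patient changes a PT row by at most one. A single worse episode, one with missing severity, or one under another LLT in the same PT restores that patient. The rate is assumed, and treatment may end before Week 244 on commercial availability.

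Third, the 91-day window is an inference. Protocol 9.2.1 says when AEs are recorded, not which period sets the baseline. Pre-existing conditions are also collected at screening in all three diseases, so the window could reach further back.

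Fourth, with about 5 patients, listings are a main tool and the all-AE listing shows onset dates. Exclusion criteria 8, 11 and 12 restrict recent zoster, serious infections and infections of unacceptable risk, so a masking infection would mostly be a milder one. Both points limit the harm. They do not restore the event to the AESI listing or to the registry Other table.

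Finally, no comparison between diseases is planned. Unequal windows are therefore a caution for reading the by-diagnosis tables side by side, and they do not invalidate an analysis.

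**Conclusion.** The point holds as an unreconciled definition with a possible undercount. If the LLT rule is applied literally, a resolved pre-dose event can keep a later episode of the same LLT, at equal or lower severity, out of three outputs: the TEAE table, the treatment-emergent AESI listing and the registry Other events. The all-AE, SAE and registry SAE outputs keep the event.

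The size cannot be computed without event rates. In the TEAE table the limit is one patient per PT for each masked patient. If all of about 5 patients form the denominator, one patient is 1/5, or 20 percentage points. Masking can be unequal by disease, with a nominal window 2.6 to 13 times as long in NNS/CANDLE, provided that the baseline period starts at consent; the factor 13 also needs the shortest permitted screening in SAVI or AGS. No decision rule depends on the flag, but the text should be settled before the final outputs are produced.

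**What to change.** Amend SAP 6.12.2.3 before the final database lock, in three parts:
- Define when the baseline period starts and ends for each disease.
- State that an AE with onset after the first dose is treatment-emergent, even if an earlier, resolved event had the same LLT.
- Use the LLT maximum severity only to judge worsening of events ongoing at the first dose.

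With this text, 0 of the 9 severity combinations lose a new episode, and the unequal windows no longer affect new onsets.

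The cost is a short SAP revision, a re-run of the TEAE flag, and possibly slightly higher TEAE counts. According to the SAP revision history and SAP 6.15, the primary-period analysis (planned to support regulatory submission) and the Week 52 analysis come before this change. The CSR should therefore state which rule those locks used and report any difference in the flag, or show both flags side by side.
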